- General wear instructions and considerations: Participants will be instructed to wear the SAM for 4-11consecutive days depending on the assessment timepoint. The SAM will be worn continuously during all waking hours, expect when bathing, showering, or swimming. The physical therapist will fill out the SAM researcher form to appropriately document the SAM calibration process for each participant. Participants will be given instructions on how to don/doff the device and will be provided with a form to record times the SAM is removed over wear period. The SAM requires no maintenance by the user besides remembering to keep it on. The physical therapist will provide strategies to help the participant remember to put the SAM back on if they do take it off at any time (e.g., if the SAM is taken off at night, place it on a nightstand next to the bed so it is seen in the morning).
- Specific wear schedule for Baseline Assessment: For the Baseline Assessment, the SAM will be worn for 4 consecutive days prior to initiating the intervention (and will continue to wear it for another 7 days during training please see next section 2. Intervention). Participants will be contacted via phone within 24-48 hours following the evaluation session to ensure that they are comfortable with the device and to address any questions or concerns. Furthermore, participants will be notified that they may contact study staff during work hours at any point during the wear period if they experience any technical issues with the SAM or have any questions.
- Operation and data download: Using the manufacturer's software, the SAM will be calibrated by a physical therapist to each participant's gait pattern based on height, typical walking speed, and leg motion. Collected data will be downloaded to a tablet computer, with which manufacturer's software will convert stride counts to step counts and calculate daily step count values. No identifiable information is collected by the SAM.

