#### 2. Intervention:

# Amped-PD: Remote Walking Program Description

(prescribed walking program of 15 hours total over six weeks + concurrent use of SAM device 4 days during early training)

**Overview:** The remote walking program is a self-directed, structured walking program held in home/community settings using the music-based device. Participants will be instructed to complete five home/community-based walking sessions per week (one session/ day, 30 minutes in duration) for six weeks. Participants may choose to perform these 5 training sessions on any days of the week according to their needs.

**Description of Walking Program:** Using the music-based device, participants will conduct the walking sessions at their self-selected pace in

a home/community environment that limits the amount of stops and/or pivot turns in order to optimize continuous walking. For the purposes of this study, home/community environment is considered any environment outside a professional healthcare facility. This includes but is not limited to the home, apartment building, independent living retirement homes, outdoor environments (tracks, parks, sidewalks), office environments and community/ recreation centers.

**Duration of Walking Session:** Each individual walking session will be completed within a 30- minute timespan (i.e., should not be split up throughout the day). Participants are allowed to rest as needed during the 30-minute training period. The time clock will continue to run down continuously once the 30 minutes are started (i.e., if a participant rests for 5 minutes, this will equate to 25 minutes of walking). Participants will be instructed to terminate any walking session in the event of technical or medical issues to allow for adequate resolution.

**Walking program diary:** Participants will be asked to record in a study diary their schedule (dates and times) of walking, location, record of any falls they experience and any comments/issues they experience while using the device (see Appendix VII: Outcome Measures).

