Physical therapy check-in call: During the baseline evaluation visit, the research team will ask the participant which time each week is preferred to have a check-in call. This phone call will last approximately 5-10 minutes to check on participant engagement in the walking program, and to provide guidance regarding any questions/concerns and/or any medical/ technical issues. If participants are unable to carry out the walking program 5- days per week, a study staff member will discuss the barriers to implementation (by phone) and suggest ways to optimize adherence to the program (e.g., setting a schedule). A study staff member will also inquire about adverse events during the weekly phone call and ensure that the participant is comfortable with the walking program.

Step Activity Monitoring: After completing 4 days of wear prior to starting training, the participant will continue to wear the SAM for an additional 7 days upon intervention initiation (total of 11 days continuous wear). During training, both the SAM and the shoe sensors of the music-based device can be worn simultaneously on the same side of the body without interfering with a participant's walking and/or increasing the risk for trips/falls. Participants will return the SAM to study personnel via a pre-labeled, addressed envelope to mail following 11 days of continuous monitoring period. The researchers will download the data and will store in a secure server.

Interruptions in training: In the event of unavoidable interruptions in training, booster sessions may be implemented to promote treatment fidelity. For training interruptions that last up to 2 weeks, the participant will continue the program and receive booster sessions at 100% of the time missed. For training interruptions of greater than 2 weeks, the training will be restarted after a reasonable washout interval, as determined by the Principal Investigator (a licensed physical therapist). If training interruption resulted in permanent change in eligibility, the participant will be withdrawn from the study.

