# 3. Second Evaluation Visit: Post-Assessment Visit (approximately 2-3 hours):

The post-intervention assessment visit will be scheduled within approximately 7 days of completion of the structured walking program and take place at the Center for Neurorehabilitation at Boston University. This visit will entail the same battery of assessments performed at Baseline Assessment including: 10MWT, 6MWT, Borg's RPE, Mini BESTest, MDS-UPDRS I/II/III, 5xSTS, PDQ-39, SRHI, GDS. Quantification of movement will be performed using wearable sensors to measure balance and walking as examined in the aforementioned battery of assessments.

Further, a usability questionnaire will be administered for those who completed Amped-PD. For both Amped-PD and Active-Control groups, participants will be asked to bring in their study diary for study personnel to review and to make a copy for their data file. This study diary will be returned to the participant for continued use if needed during the Follow-up Period. For the Amped-PD group, they will have continued access to the music-based device during the Follow-up Period. The SAM monitor will be given to the participant to wear for 7 days during Follow-Up Training. Participants who withdraw or are withdrawn prior to completing their last walking session may be asked to complete closing visit activities, if feasible.

4. Follow-Up Walking Program (2 weeks): Extended Remote Walking Program

Description for both groups (recommended continuation of routine walking + concurrent use of SAM device 4 days during follow-up training)

**Overview:** Participants in both Amped-PD and Active-Control groups will be recommended to carry out the walking program independently for another 2 weeks,

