## **Statistical Analysis Plan**

We will use parametric statistics to data with normal distribution verified using Shapiro-Wilk test and to data that meet the assumptions of homogeneity of variances using Levene's test. Otherwise, non-parametric statistics will be used.

To examine between-group differences for all primary outcomes (moderate intensity minutes, daily steps, stride time variability, and habit strength), we will run a one-way ANOVA or Kruskall-Wallis test to compare change scores at the 6-Week and 8-Week clinical assessments relative to baseline.

To examine within-group differences for all primary outcomes (moderate intensity minutes, daily steps, stride time variability, and habit strength), we will run a Repeated Measures ANOVA or Friedman's ANOVA on absolute values of all primary outcomes across their respective timepoints, with multiple post-hoc comparisons corrected using Bonferroni adjustments.

For all secondary outcomes, we will perform between-group analyses using non-parametric statistics to compare change scores at the 6-Week and 8-Week clinical assessments relative to baseline, using two-tailed tests with alpha set at 0.05.

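### The step-monitor baseline uses only 4 of the 11 days worn, so the change scores for daily steps and moderate-intensity minutes are noisier than the same wear could give

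*Protocol*

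**What the plan says.** Under 1.b Baseline Assessment (Walking Activity), "the SAM will be worn for 4 consecutive days prior to initiating the intervention". Under Step Activity Monitoring in the Amped-PD programme, which the Active-Control section adopts, participants then "continue to wear the SAM for an additional 7 days upon intervention initiation (total of 11 days continuous wear"). The split is therefore 4 days before training and 7 after it starts.

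Two later windows follow. At the Post-Assessment visit, "The SAM monitor will be given to the participant to wear for 7 days during Follow-Up Training". After the final visit the monitor is worn for 4 more days (Step Activity Monitoring, at the end of section 4).

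The day counts are not consistent. The line under each arm's programme heading gives "concurrent use of SAM device 4 days during early training", against 7 in the text. The Follow-Up Walking Program heading gives "concurrent use of SAM device 4 days during follow-up training", against 7 in the Post-Assessment text.

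The SAP names four primary outcomes. Two of them, daily steps and moderate-intensity minutes, are taken here to come from the step monitor. The between-group test is to "compare change scores at the 6-Week and 8-Week clinical assessments relative to baseline". A separate within-group repeated-measures or Friedman ANOVA covers each outcome's timepoints, which the SAP does not list. The documents give no reason for a 4-day baseline, no minimum number of valid days and no weekday/weekend rule.

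**The concern.** The baseline mean is subtracted in every change score for the two step-monitor outcomes, so its day-to-day noise enters both the 6-week and the 8-week comparison. Yet it is the shorter part of the first wear run. The longer part is a week that is neither a 6-week nor an 8-week value. In a 44-person trial that tests unadjusted change scores, this noise lowers power on two of four primary outcomes. Much of it could be avoided without asking participants to wear the monitor longer.

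**Working it through.** The documents state no effect size, SD or power, so there is no planned calculation to reproduce.

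**Inputs from the documents**
- Baseline days b = 4.
- Later days f = 7 (issued at the Post-Assessment visit) or f = 4 (after the final visit). The SAP does not say which window supplies which value. I take the 7-day window as the 6-week value and the 4-day window as the 8-week value.
- 44 participants with balanced allocation, taken as 22 per arm.
- Two-sided alpha of 0.05. The SAP states this only for secondary outcomes; it is assumed here for the primary ones.

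**Inputs assumed**
- Day-to-day SD s = 1,500-3,000 steps (middle 2,500).
- SD of true change t = 1,000-2,000 steps (middle 1,500).
- Between-group difference of 1,500 steps/day.
- Days roughly independent.

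**Formula.** Var(change) = s²(1/b + 1/f) + t².

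**Share of day-level noise due to the baseline.** With b = 4 and f = 7, 1/4 + 1/7 = 0.393, of which the baseline supplies 0.250/0.393 = 64%. With f = 4, it supplies 0.250/0.500 = 50%.

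**Middle case (s = 2,500, t = 1,500)**
- 6 weeks, b = 4: 6,250,000 × 0.3929 + 2,250,000 = 4,705,357, SD 2,169.
- 6 weeks, b = 7: 6,250,000 × 0.2857 + 2,250,000 = 4,035,714, SD 2,009. Variance falls by 14.2%.
- 8 weeks, b = 4: 6,250,000 × 0.5 + 2,250,000 = 5,375,000, SD 2,318.
- 8 weeks, b = 7: 6,250,000 × 0.3929 + 2,250,000 = 4,705,357, SD 2,169. Variance falls by 12.5%.

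**Power.** Two-sample t-test, 42 degrees of freedom, noncentrality 1,500/(SD × √(2/22)).

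| Contrast | Case (s / t) | Variance cut, b = 4 to 7 | Power, b = 4 | Power, b = 7 |
|---|---|---|---|---|
| 6 weeks (f = 7) | smallest cut (1,500 / 2,000) | 4.9% | 0.595 | 0.616 |
| 6 weeks | middle (2,500 / 1,500) | 14.2% | 0.611 | 0.677 |
| 6 weeks | largest cut (3,000 / 1,000) | 21.3% | 0.626 | 0.730 |
| 8 weeks (f = 4) | smallest cut (1,500 / 2,000) | 4.7% | 0.574 | 0.595 |
| 8 weeks | middle (2,500 / 1,500) | 12.5% | 0.554 | 0.611 |
| 8 weeks | largest cut (3,000 / 1,000) | 17.5% | 0.545 | 0.626 |

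At 6 weeks the gain equals about 5-27% more participants (1/0.951 = 1.05 to 1/0.787 = 1.27).

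**Effect on the early-training contrast.** Baseline against the first training week has day-level variance s²(1/4 + 1/7) now. With a 7 + 4 split it has s²(1/7 + 1/4), which is the same.

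**Weekend composition.** By start day from Monday to Sunday, 4 consecutive days hold 0, 0, 1, 2, 2, 2, 1 weekend days. The SD of the weekend fraction is 0.208. If weekend days differ by an assumed 1,000 steps, that is 208 steps/day, and (208/2,169)² = 0.9% of the middle-case variance.

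**Partly worn days.** A day with half its steps recorded lowers a 4-day mean by 0.5/4 = 12.5% and a 7-day mean by 0.5/7 = 7.1%, if days are otherwise equal.

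The calculations are in steps. The same formula applies to moderate-intensity minutes, but no sizes were worked out for them.

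**The case against.** That more baseline days give less noise is true of any design, and the size here rests wholly on assumed SDs. In SD terms the 6-week gain is only 2.5-11%, and in the smallest case power moves by 2 points. That stands, and it limits the priority.

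A reader might infer that the seven training days are wasted. The documents do not support this. The within-group ANOVA may use the first training week, and Figure 1, which might show the timepoints, is not reproduced in the text reviewed. What can be said is that the week does not enter the between-group test.

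A reader might also take free choice of training days ("Participants may choose to perform these 5 training sessions on any days of the week according to their needs") as a reason for a longer baseline. It is not one, because the baseline precedes training and holds no programme sessions. The variation belongs to short windows during training, and a 7 + 4 split would create one. With 5 sessions in 7 days, a 4-day window holds 2, 3 or 4 of them in 6, 12 and 3 of the 21 arrangements. The SD is 0.639 sessions. At an assumed 3,000 steps per session that is 0.639 × 3,000/4 = 479 steps/day.

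Two further objections stand. The 4-day window after the final visit limits the 8-week contrast as much as the baseline does, and a longer baseline leaves it untouched. Section 1 also describes baseline tests, randomization and device training with no later pre-training visit. If monitor wear follows randomization and device handover, a longer baseline lengthens the time in which participants know their arm before training starts.

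**Conclusion.** The point holds as an efficiency loss on two primary outcomes. Its direction needs only non-zero, roughly independent day-to-day variation. Its size cannot be fixed from the documents: under the stated assumptions the avoidable variance is about 5-21% at 6 weeks and 5-18% at 8 weeks, with power gains of about 2-10 and 2-8 points.

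It should not be read as bias, since both arms follow the same windows. Nor should weekend composition be given much weight: it is under 1% of variance in the middle case, and the day-to-day SD probably includes it already. The 11-day total is explicit in the text, but the programme headings imply 4 + 4 = 8 days, so the proposal to keep total wear unchanged depends on resolving that conflict. Priority is low to moderate.

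**What to change.** 1. **Reconcile the wear schedule.** Early training is given as 4 days under both arms' programme headings and as 7 in the text. Follow-up is given as 7 days in the Post-Assessment text and as 4 in the follow-up heading. State which window supplies the 6-week value and which the 8-week value.
2. **Split the 11-day run as 7 days before training and 4 after it starts.** This matches the 4 early-training days in the headings and adds no wear if 11 days is the intended total.
3. **Optionally, in the SAP,** analyse day-level values in a mixed model with a weekday/weekend term. Add a valid-day rule based on the removal form already collected, fixed before outcomes are examined by arm. Neither step needs a change in wear. Adjusting for baseline in place of raw change scores would also reduce the effect of baseline noise without altering the schedule.

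**Cost.** Short edits to the protocol and SAP. Training starts 3 days later. The early-training window no longer spans a full programme week, so it carries session-count noise, which matters if the within-group ANOVA uses it. If wear follows randomization and device handover, participants know their arm for 3 more days of the baseline period.

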# 1.d Device Training Amped-PD Intervention:

# Training Procedures / Instruction to Participants:

# Music-Based Device Training (Only for Amped-PD)

Participants who are randomized to receive Amped-PD intervention will undergo training on how to use how to use the music-based device and independently conduct the remote walking program. The music-based device (MedRhythms, Portland, ME) is specifically designed for gait training in people with neuromotor impairments. Participants will be trained to independently use the device. A simple setup which takes < 2 min involves initiating the smartphone application, wearing the headphones, and attaching a movement sensor to the outer side of each shoe below the ankle. The smartphone is kept in the user's pocket throughout the session. The music-based device obtains real-time walking information through the shoe sensors that communicate wirelessly with the smartphone application software. The music-based device delivers music cues that are adjusted according to the user's walking pace as detected by the shoe sensors. These music cues serve as the substrate for rhythmic auditory stimulation during walking.

Training with the music-based device will be administered after completing the In-person screening and Baseline Assessment procedures. To ensure that the participant is able to hear the music, the physical therapist will have the participant put on the headphones while music is played. The physical therapist will instruct participants to listen to the music at a safe volume so they can still hear sounds in their environment. The participant will then practice donning/doffing, adjusting the volume, setting up, and using the device (i.e., walk for 5 minutes) to demonstrate comprehension and independent use. A team member will provide the participant with the necessary equipment (i.e., smartphone, shoe sensors, headphones, study diary). The physical therapist will be able to determine safe and independent walking ability during the 5 minutes of walking with the device. Five minutes is enough time for the participant to experience an increase in music tempo and for the physical therapist to determine if guarding is needed during these transitions. At the end of this training period, if the physical therapist determines that the participant will need continued assistance from another person to walk and perform transitions (i.e. turns, step initiation) while using the music-based device, the participant will be withdrawn from the study. Otherwise, the physical therapist will proceed and discuss the space and location in which the participant plans to conduct the walking program, and review space adequacy and safety considerations. A safe environment will be considered to be the following: indoor spaces - level surfaces, obstacle-free, no slippery surfaces, no unsecure area rugs; outdoor spaces – avoid auto or bike traffic, obstructive tree roots, divots in the asphalt and concrete. These environments could include, but are not limited to: home, apartment building hallway, neighborhood sidewalks, local track or park, office environments, and community/ recreation centers. Ideally the space is at least 50 feet in length that meet the above indoor and outdoor space criteria. This will decrease

the amount of pivot turns thereby optimizing the amount of continuous walking. The purpose of the music-based device is to help participants entrain to a musical beat to improve the quality of their walking. Leveraging the benefits of RAS such as increased stride length, cadence, and speed enable walking at faster speeds and higher intensities, thus making it advantageous to perform greater amounts of walking at moderate intensities – an important health objective set forth by guidelines by public health and clinical practice sectors. The device monitors a participant's cadence using the sensor placed on the shoe. The musical tempo is matched to the baseline walking cadence of the participant. As the quality of a participant's walking improves and the participant accurately "entrains" to the tempo of the music, the tempo will adapt and increase cadence by 5%. For example, if the participant starts off walking 100 steps/minute, once considered entrained, the tempo will increase to 105 steps/minute. This increase is very small and will most likely not be noticed by the participant. If the participant is unable to increase their cadence to match this tempo, the tempo is reduced back to baseline. The algorithm used to set the tempo is dynamic and adjusts to the cadence of the participant. If a participant feels that they cannot keep up with the faster cadence, they can continue walking at their comfortable pace. Participants will also be instructed to stop the intervention if they feel uncomfortable or anxious at any time.

Following this training, it is expected that participants will be able to independently setup (including donning/doffing the device), perform and conclude a walking session independently. Participants will have access to Instructions for Use (IFU) that will detail all procedures required for proper operation of the system. However, participants will be encouraged to contact the research team if they have any additional questions, issues or concerns. Participants will be excluded from the study if unable to demonstrate how to use the device independently as determined by the physical therapist. Please note, participants will be provided with a preestablished username and password. No personally identifiable information will be recorded or stored in the device application.

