# 1. First Evaluation Visit: In-Person Screening & Baseline Assessment Visit (approximately 2-3 hours):

The in-person screening and baseline assessment visit will take place at the Center for Neurorehabilitation at Boston University. All participants will have completed and provided their informed consent prior to Screening and Baseline Assessment (see Appendix II: Informed Consent; see section K). After consenting, participants will be asked to sign a HIPAA Authorization to Disclose Protected Health Information for Research Purposes (see Appendix III: HIPAA Authorization). This will allow our team to communicate directly with the participant's healthcare provider during the study if needed.

**1.aIn-Person Screening**: An in-person Screening will be administered to determine if participants meet all study inclusion/exclusion criteria. The elements included in the screening process are part of routine physical therapy evaluation. A physical exam will be conducted to assess cognitive status, Parkinson's symptoms and walking capacity.

- 1. A diagnosis of Parkinson disease will be confirmed per participant report.
- 2. The Mini-Mental State Exam (MMSE) will be administered to screen for significant cognitive impairment (exclude MMSE score < 24) (see Appendix VI: Screening Tools). The MMSE is a brief screening tool that examines cognitive impairment. Participants are tested on 11 items that cover multiple cognitive domains. The score ranges from 0-30, with higher scores indicating less cognitive impairment.

- Disease severity will be assessed by a licensed physical therapist using the Modified
- 4. Hoehn & Yahr Scale (only H&Y 1-3 will be included) (see Appendix VI: Screening Tools). The Modified H&Y Scale includes additional criteria to rate Parkinson disease symptoms on a scale from 1 to 5. Higher scores indicate increased disease progression.
- 5. Walking capacity assessments instrumented with wearable sensors:
  - The following tests on walking will be instrumented with in-lab movement sensors (XSENS, Enschede, the Netherlands), which will be worn on both mid-shank (2) and mid-thigh (2) areas, and on mid-

line low-back area (1), and the sensors of the music-based device (MedRhythms, Portland, ME), which will be secured on to the outer sides of the shoes (2). The other components of the music-based device such as its audio-cue mechanism and headphones will not be used during this screening procedure.

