- 1.cRandomization: At the completion of procedures for Baseline Assessment, the participant will be randomized to receive either the experimental or control arm of the intervention. The experimental arm, called Amped-PD, is a 6-week community-based structured walking program that uses a music-adaptive RAS followed by 2 weeks of unstructured walking protocol (continue as desired) for a total of 8 weeks. The control arm, called Active-Control is a similarly structured 6-week community-based walking program that does not use RAS, followed by 2 weeks of unstructured walking protocol (continue as desired) for a total of 8 weeks of training. Block randomization with balanced allocation between the two groups will be implemented. A randomization list will be generated prior to enrollment of participants. The researcher will gain knowledge of treatment assignment only after procedures in In- person Screen and Baseline Assessments have been completed.

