# Active-Control Intervention: Remote Walking Program Description

(Prescribed walking program of 15 hours total over six weeks + concurrent use of SAM device 4 days during early training)

**Overview:** The Active-Control Intervention is similarly structured as Amped-PD Intervention, with the only exception of not using RAS/ music-based device. Participants will be instructed to complete five home/community-based walking sessions per week (one session/ day, 30 minutes in duration) for six weeks.

**Description of Walking Sessions:** Without using the music-based device, participants will conduct the walking sessions at their self-selected pace in a home/community environment. All other considerations as outlined above apply to this intervention.

**Duration of Walking Session:** Each individual walking session will be completed within a 30- minute timespan (i.e., should not be split up throughout the day. Participants will be asked to use their own wristwatch,

timer, or cellphone to monitor the time/ duration of walking session. Participants are allowed to rest as needed during the 30-minute training period.

**Walking program diary:** Participants will be asked to record in a study diary their schedule (dates and times) of walking, location, record of any falls they experience and any comments/issues they experience while performing the walking program.

**Safety Considerations:** Same as above as outlined in Amped-PD. **Physical therapy check-in call:** Same as above as outlined in Amped-PD. **Step Activity Monitoring:** Same as above as outlined in Amped-PD.

Interruptions in training: In the event of unavoidable interruptions in training, booster sessions may be implemented to promote treatment fidelity. For training interruptions that last up to 2 weeks, the participant will continue the program and receive booster sessions at 100% of the time missed. For training interruptions of greater than 2 weeks, the training will be restarted after a reasonable washout interval, as determined by the Principal Investigator (a licensed physical therapist). If training interruption resulted in permanent change in eligibility, the participant will be withdrawn from the study.

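### Two device-check rules remove randomised participants from the Amped-PD arm only, with no assured follow-up and no stated analysis set

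*Protocol*

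**What the plan says.** Protocol section 1.c places allocation after baseline: "At the completion of procedures for Baseline Assessment, the participant will be randomized". Section 1.d then describes training for one arm: "Participants who are randomized to receive Amped-PD intervention will undergo training". Two removal rules follow from that training.

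- **Assistance.** This covers anyone the therapist judges to need another person's continuing help to walk and make transitions: "while using the music-based device, the participant will be withdrawn from the study".
- **Handling.** "Participants will be excluded from the study if unable to demonstrate how to use the device independently as determined by the physical therapist".

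The check is not just a repeat of screening. In section 1.a the shoe sensors are worn, but the device's "audio-cue mechanism and headphones will not be used during this screening procedure". In section 1.d, five minutes of cued walking is considered long enough "for the physical therapist to determine if guarding is needed during these transitions", the transitions being the rises in music tempo.

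The Active-Control programme is built the same way, "with the only exception of not using RAS/ music-based device", so it has no counterpart to either rule. For people withdrawn before their last walking session, section 3 (Post-Assessment Visit) allows a closing visit but does not require one. The SAP compares change scores at 6 and 8 weeks with baseline. It defines no analysis set and gives no missing-data method.

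**The concern.** Randomisation makes the arms comparable only if the people randomised are the people compared. Here a judgement made after allocation, by someone who knows it, can take people out of one arm. If those who fail the check would have changed differently over 6 or 8 weeks, the remaining Amped-PD participants no longer match the full Active-Control arm, and the difference between arms includes that mismatch.

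The direction cannot be read from the documents. People who struggle with the device may be weaker walkers, but the analysis uses change scores, and weaker walkers may gain more or less than others. Outcomes not collected at 6 and 8 weeks cannot be recovered later. An analysis set chosen once the removals are known would leave discretion in a trial of 44.

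A side point depends on timing that the text does not settle. If device training happens at the first visit, before the 4-day step-monitor wear described in section 1.b, those removed could also lack baseline daily steps and moderate-intensity minutes. If the wear is finished before randomisation, which sections 1.b and 1.c also allow, this does not arise.

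**Working it through.** **Inputs from the documents.** Enrolment is 44 (Study Design) with balanced block allocation (1.c), so 22 per arm is inferred. Two-sided 0.05 is stated in the SAP for secondary outcomes only and is assumed here for the primary ones. The documents give no effect size, SD, power or dropout, so the figure of 44 cannot be reproduced. The structural point does not depend on it.

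**Assumed inputs.** The device-check failure rate p is 2%, 5% or 10%. The correlation rho between device ability and the change score is 0 or ±0.5. There is no treatment effect. Results are in SDs of the change score, using a pooled t-test; the SAP's Kruskal-Wallis branch was not simulated.

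**1. How many removals.** Expected number = 22p. Chance of none = (1−p)^22.

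**2. Bias averaged over trials with and without removals.** If the lowest fraction p on device ability is removed, the mean of those kept shifts by rho × φ(z_p)/(1−p), where φ is the standard normal density at the p-quantile. At p = 0.05 this is 0.5 × 0.1031/0.95 = 0.054.

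| p | Expected removals | Chance of none | Shift at rho = 0.5 | Simulated type I error |
|---|---|---|---|---|
| 2% | 0.4 | 0.64 | 0.025 | 0.051 |
| 5% | 1.1 | 0.32 | 0.054 | 0.053 |
| 10% | 2.2 | 0.10 | 0.097 | 0.061 |

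**3. Bias given exactly k removals.** The three lowest of 22 standard normal scores have means −1.910, −1.459 and −1.189. The shift is rho × (sum of the k lowest, sign reversed)/(22−k).

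- k = 1: 0.5 × 1.910/21 = 0.045
- k = 2: 0.5 × 3.369/20 = 0.084
- k = 3: 0.5 × 4.558/19 = 0.120

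Simulated type I error is about 0.054, 0.060 and 0.070. At rho = −0.5 the sizes are the same and the sign reverses, favouring control. At rho = 0 the error rate stays at 0.050.

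**4. Cross-check by another route.** If the removed differ from the kept by D, bias = (k/22) × D, with standard error √(1/(22−k) + 1/22). For k = 2 in step 3, the removed average −0.5 × 3.369/2 = −0.842, so D = 0.842 + 0.084 = 0.926 and (2/22) × 0.926 = 0.084, as before. Taking D from 0.5 to 1.0 gives 0.02 to 0.05 SD for one removal, 0.05 to 0.09 for two and 0.07 to 0.14 for three. The normal-approximation error rate then runs from 5.1% to 7.2%.

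**5. Power if those removed are kept in the analysis.** With 22 per arm, 80% power corresponds to an effect of 0.865 SD. If k people never start the device and gain nothing over control, the effect becomes 0.865 × (1−k/22), a dilution of 1/22 = 4.5% to 3/22 = 13.6%.

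| k | Power, kept as randomised | Power, removed (22−k v 22) | Difference |
|---|---|---|---|
| 1 | 0.762 | 0.790 | 0.028 |
| 2 | 0.721 | 0.780 | 0.058 |
| 3 | 0.677 | 0.768 | 0.091 |

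**6. Partial follow-up.** At rho = 0.5, if one of two removed people returns for assessment, the remaining shift is 0.842/21 = 0.040, about half of 0.084. If all return, it is zero.

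**The case against.** **Screening leaves little for the rules to catch.** Before randomisation both arms are screened on MMSE, 10-minute walking tolerance and need for guarding. They are also screened on falls, freezing, hearing and walking without assistance. Set-up takes under 2 minutes, the tempo step is 5%, and it reverts if not matched. This stands as the reason to expect few removals. It does not remove the point: cued walking and independent handling are first tested after randomisation, and no screen covers device handling.

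**The numbers rest on assumed inputs.** True. At rho = 0.3 the step 3 formula gives 0.03, 0.05 and 0.07 SD for 1, 2 and 3 removals, with type I error below 0.06. At a 2% failure rate the likeliest result is no removal at all. This supports calling the effect small, but the rule still acts on one arm only.

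**This is just a general gap in the SAP.** In part. The missing analysis set affects every dropout in both arms. What is specific here is a written rule that creates loss in one arm only.

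**Other text may cover it.** The supplied protocol breaks off mid-sentence in section 4, and neither the section K it cites nor its list of exclusion criteria is included. However, section 3 does address withdrawn participants and leaves their follow-up optional, and the SAP reads as complete.

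**Keeping people in may cost more than step 5 shows.** This is correct if they do worse than controls. If they change 0.5 SD less, the effect is 0.865 × (1−k/22) − 0.5k/22, and power is roughly 0.74, 0.67 and 0.6.

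**Conclusion.** The concern holds and should be fixed. The order of events, the restriction to one arm, the optional follow-up and the absence of an analysis set are all plain in the text. The distortion is probably small. Averaged over the assumed failure rates, it is 0.02 to 0.10 SD, with type I error between 0.051 and 0.061. It is modest if as many as three people are removed. The sign is unknown. These sizes rest on an inferred 22 per arm, failure rates and a correlation that the documents do not give, and a t-test. The structural finding rests on none of them. The case for acting is that the remedy is cheap and the lost outcomes cannot be recovered.

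**What to change.** Leave both criteria for not using the device as they are, and separate stopping the device from leaving the study.

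1. **Protocol 1.d.** Replace withdrawal or exclusion from the study with a statement that the person does not use the device but stays in for outcome assessment unless consent is withdrawn. The sponsor should also state what such a person does during the walking period; that is a clinical decision and is not proposed here.
2. **Protocol section 3.** Turn the optional request into a definite one and list what is sought: baseline step-monitor wear if not yet done, the 6- and 8-week assessments timed from randomisation, and the monitor wear tied to them.
3. **SAP.** Analyse all randomised participants in their assigned arm. Name the missing-data method, for example multiple imputation from baseline and arm, with a sensitivity analysis imputing those who never started the device from Active-Control. Say how this works if the non-parametric branch is used. Report removals by arm with reasons.

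**Cost.** Beyond the wording, 1 to 3 people attend 2 further visits of 2–3 hours, taking the 8-week visit to be as long as the 6-week one: 1×2×2 = 4 to 3×2×3 = 18 participant-hours, plus monitor wear. The clinic walking tests are already guarded. The net power cost is about 3 to 9 points if those retained do as well as controls, and more if they do worse. The analysis then estimates the effect of assignment, not the effect in people able to use the device. The bias is removed only as far as outcomes are obtained.

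**Option.** Give every candidate the same device check after the clinic baseline tests and before randomisation, and still make changes 2 and 3. This adds about 10–15 minutes (assumed), including 5 minutes of cued walking for future controls, or 5/900 = 0.6% of the 15-hour programme. It narrows the population slightly and requires a change to the screening statement on the audio cue. It also lets controls try a device they will not receive, which could affect self-reported habit strength.
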